9.2.2 Intranasal Administration of Rhinovirus

All randomized participants will be administered HRV-16 intranasally on Day 1. A detailed description of the preparation and administration of HRV-16 is provided in the Procedures Manual.

If there is no confirmation of viral infection within 72 hours post-inoculation with HRV-16 by PCR assay, the participant will be discontinued from treatment.

The trial site will be responsible for recording the lot number, manufacturer, and expiry date of applicable supplies related to HRV-16 administration.

Note: Participants will receive the first dose of study treatment immediately after administration of HRV-16. There is no requirement for participants to display symptoms of infection prior to administration of first dose of trial treatment.

9.2.3 ATP Cough Challenge (Stage 1 Only)

Cough reflex sensitivity is measured by standard clinical methodology incorporating ATP cough challenge in accordance with the Procedures Manual. The ATP cough challenge will be administered ONLY during Stage 1 of the trial.

The standard endpoints measured in cough challenge testing are reflex sensitivity to ATP measured by C2 and C5 (ie, concentration of cough challenge agent [ATP] inducing at least 2 or 5 coughs, respectively) during Stage 1 on Days -1, 1, 4, and 7.

The number of coughs during the ATP cough challenge will be assessed manually by site staff during all ATP cough challenges.

Participants will continue to wear the cough monitor during the cough challenge procedures on Days 1, 3, and 7, as the cough counting data from the cough monitor will be used to support the primary analysis. All analyses related to the ATP cough challenge will be performed using manual cough counting data, including the exploratory analysis related to cough reflex sensitivity.

The challenge should be discontinued for the day if a participant experiences severe side effects or coughs excessively and makes a clear request to stop taking the challenge test (see Procedures Manual).

β -agonist should be available for participants who experience bronchoconstriction; other appropriate medical interventions should be provided as necessary. Those who need to discontinue the cough challenge may still participate in the cough challenges on subsequent days.

9.2.4 Patient-reported Outcomes

At Baseline (Day -1), each participant will be properly trained and instructed on the completion of all PRO assessments/questionnaires: CSD, Cough Severity VAS, LCQ-acute, and WURSS-24. These assessments/questionnaires should be provided to the participant and conducted in the same order each day at approximately the same time in the evening, as specified in the SoA (Section 2.0). Data must be reviewed by the investigator or designee each time a participant completes an assessment/questionnaire. Overall completeness and accuracy of all recorded entries should be reviewed. Deficiencies should be immediately discussed with the participant to improve the quality of future assessment/questionnaire entries. The investigator and qualified designee should ensure that any relevant comments that refer to possible AEs are discussed or clarified with the participant, and any AEs are collected in the AE electronic case report form (eCRF).

9.2.4.1 Cough Severity Diary

Participants are instructed to record their cough frequency, intensity, and associated disruptions using the 7-item CSD. Participants will rate each item using an 11-point scale ranging from 0 to 10, with higher scores indicating greater severity of cough.

9.2.4.2 Cough Severity Visual Analog Scale

Participants are instructed to rate the severity of their cough “today” using a 100 mm VAS single-item questionnaire with the response ranging from 0 (“no cough”) to 100 (“extremely severe cough”).

9.2.4.3 Leicester Cough Questionnaire-Acute

Participants are instructed to complete the 19-item LCQ-acute to assess the impact of their cough severity in the last 24 hours on physical, social, and psychological functioning, using a 7-point Likert scale ranging from 1 to 7; higher scores indicate better HRQoL.

9.2.4.4 Wisconsin Upper Respiratory Symptom Survey-24

Participants are instructed to complete the WURSS-24 questionnaire, an illness-specific quality of life instrument designed to assess the negative impact of acute URTI, using an 8-point Likert scale ranging from 0 to 7; higher scores indicate worse HRQoL. Influenza-like illness symptoms of headache, body aches, and fever are included on the WURSS-24.

9.3 Adverse Events (AE), Serious Adverse Events (SAE) and Other Reportable Safety Events

The definitions of an adverse event (AE) or serious adverse event (SAE), as well as the method of recording, evaluating, and assessing causality of AE and SAE and the procedures for completing and transmitting AE, SAE and other reportable safety event reports can be found in Appendix 4.

AE, SAEs, and other reportable safety events will be reported by the participant (or, when appropriate, by a caregiver, surrogate, or the participant's legally authorized representative).

The investigator, who is a qualified physician, and any designees are responsible for detecting, assessing, documenting, and reporting events that meet the definition of an AE or SAE as well as other reportable safety events. Investigators remain responsible for following up AE, SAEs and other reportable safety events for outcome according to Section 9.3.3.

Adverse events will not be collected for participants during the pre-screening period (for determination of archival tissue status) as long as that participant has not undergone any protocol-specified procedure or intervention. If the participant requires a blood draw, fresh tumor biopsy etc., the participant is first required to provide consent to the main study and AEs will be captured according to guidelines for standard AE reporting.

9.3.1 Time Period and Frequency for Collecting AE, SAE and Other Reportable Safety Event Information

All AEs, SAEs and other reportable safety events that occur after the consent form is signed but before treatment allocation/randomization must be reported by the investigator if the participant is receiving placebo run-in or other run-in treatment, if the event causes the participant to be excluded from the study, or is the result of a protocol-specified intervention, including but not limited to washout or discontinuation of usual therapy, diet, or a procedure.

From the time of treatment allocation/randomization through 14 days following cessation of treatment, all AEs, SAEs and other reportable safety events must be reported by the investigator.

Additionally, any SAE brought to the attention of an investigator at any time outside of the time period specified in the previous paragraph must be reported immediately to the Sponsor if the event is considered to be drug-related.

Investigators are not obligated to actively seek AE or SAE or other reportable safety events in former study participants. However, if the investigator learns of any SAE, including a death, at any time after a participant has been discharged from the study, and he/she considers the event to be reasonably related to the study treatment or study participation, the investigator must promptly notify the sponsor.

All initial and follow-up AEs, SAEs and other reportable safety events will be recorded and reported to the sponsor or designee within the timeframes as indicated in [Table 3](#).

Table 3 Reporting Time Periods and Timeframes for Adverse Events and Other Reportable Safety Events

Type of Event	Reporting Time Period: Consent to Randomization/ Allocation	Reporting Time Period: Randomization/ Allocation through Protocol-Specified Follow-up Period	Reporting Time Period: After the Protocol Specified Follow-up Period	Timeframe to Report Event and Follow-up Information to SPONSOR:
Non-Serious Adverse Event (NSAE)	Report if: - due to protocol-specified intervention - causes exclusion - participant is receiving placebo run-in or other run-in treatment	Report all	Not required	Per data entry guidelines
Serious Adverse Event (SAE)	Report if: - due to protocol-specified intervention - causes exclusion - participant is receiving placebo run-in or other run-in treatment	Report all	Report if: - drug/vaccine related. (Follow ongoing to outcome)	Within 24 hours of learning of event
Pregnancy/Lactation Exposure	Report if: - due to intervention - causes exclusion	Report all	Previously reported – Follow to completion/termination; report outcome	Within 24 hours of learning of event
Event of Clinical Interest (require regulatory reporting)	Report if: - due to intervention - causes exclusion	Report - Potential drug-induced liver injury (DILI) - Require regulatory reporting	Not required	Within 24 hours of learning of event
Event of Clinical Interest (Do not require regulatory reporting)	Report if: - due to intervention - causes exclusion	Report - non-DILI ECIs and those not requiring regulatory reporting	Not required	Within 5 calendar days of learning of event

Type of Event	Reporting Time Period: Consent to Randomization/ Allocation	Reporting Time Period: Randomization/ Allocation through Protocol-Specified Follow-up Period	Reporting Time Period: After the Protocol Specified Follow-up Period	Timeframe to Report Event and Follow-up Information to SPONSOR:
Cancer	Report if: - due to intervention - causes exclusion	Report all	Not required	Within 5 calendar days of learning of event
Overdose	Report if: - receiving placebo run-in or other run-in medication	Report all	Not required	Within 5 calendar days of learning of event

9.3.2 Method of Detecting AE, SAE and Other Reportable Safety Events

Care will be taken not to introduce bias when detecting AE and/or SAE and other reportable safety events. Open-ended and non-leading verbal questioning of the participant is the preferred method to inquire about AE occurrence.

9.3.3 Follow-up of AE, SAE and Other Reportable Safety Event Information

After the initial AE/SAE report, the investigator is required to proactively follow each participant at subsequent visits/contacts. All AE, SAE and other reportable safety events including pregnancy and exposure during breastfeeding, ECI, Cancer and Overdose will be followed until resolution, stabilization, until the event is otherwise explained, or the participant is lost to follow-up (as defined in Section 8.3). In addition, the investigator will make every attempt to follow all non-serious AEs that occur in randomized participants for outcome. Further information on follow-up procedures is given in Appendix 4.

9.3.4 Regulatory Reporting Requirements for SAE

- Prompt notification (within 24 hours) by the investigator to the sponsor of SAE is essential so that legal obligations and ethical responsibilities towards the safety of participants and the safety of a study treatment under clinical investigation are met.
- The sponsor has a legal responsibility to notify both the local regulatory authority and other regulatory agencies about the safety of a study treatment under clinical investigation. All Adverse Events will be reported to regulatory authorities, IRB/IECs and investigators in accordance with all applicable global laws and regulations, ie, per ICH Topic E6 (R1) Guidelines for Good Clinical Practice.

- Investigator safety reports must be prepared for suspected unexpected serious adverse reactions (SUSAR) according to local regulatory requirements and sponsor policy and forwarded to investigators as necessary.
- An investigator who receives an investigator safety report describing an SAE or other specific safety information (eg, summary or listing of SAE) from the sponsor will file it along with the Investigator's Brochure and will notify the IRB/IEC, if appropriate according to local requirements.

9.3.5 Disease-Related Events and/or Disease-Related Outcomes Not Qualifying as AEs or SAEs

There are no disease-related events and/or disease-related outcomes not qualifying as AEs or SAEs.

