The risks and side effects related to this trial are expected to be manageable. Because HRV-16 causes the common cold, participants can expect to have a combination of one or more of the following symptoms after inoculation with the virus: runny nose, itchy nose, congested nose, sneezing, itchy eyes, headache, low-grade fever, sore throat, and/or cough. During the course of treatment, participants will be medically monitored 24 hours a day at a clinic. During the ATP cough challenge, β -agonist will be available if participants experience bronchoconstriction; if this type of treatment is required, participants will not be exposed to further cough challenges on that day, but may participate in the cough challenges on subsequent days. Appropriate medical intervention will be provided throughout the trial, as needed.

Additional details regarding specific benefits and risks for participants participating in this clinical study may be found in the accompanying IB and informed consent documents (Section 3.2).

4. Objectives/Hypotheses and Endpoints

In this study, the objectives and endpoints will be evaluated in healthy adult participants with induced viral URTI as indicated in the following table. Since this is an exploratory study, hypotheses are not applicable.

Objective(s)/Hypotheses	Endpoint(s)
Primary	
Objective: To evaluate the efficacy of MK-7264 on cough frequency as measured while awake over a 24-hour period	Awake cough frequency (coughs per hour) on Day 3, as assessed by an objective cough-counting device
Secondary	

 Objective: To evaluate the efficacy of MK-7264 on the perception of cough severity 	
 Cough Severity VAS score measured as change from baseline on Day 3 CSD score measured as change from baseline on Day 3

 Objective: To evaluate the efficacy of MK-7264 on cough-specific quality of life 	
 LCQ-acute score measured as change from baseline on Day 3

 Objective: To evaluate the safety and tolerability of MK-7264 	
 Number of participants experiencing AEs Number of participants discontinuing study treatment due to AEs
Exploratory	

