For this protocol, a composite endpoint of taste-related AEs (including dysgeusia, ageusia, and hypogeusia, as well as other related terms) is considered a Tier 1 event. In addition, the broad clinical and laboratory AE categories consisting of the percentage of participants with any AE, a drug-related AE, an SAE, an AE which is both drug-related and serious, any oral paresthesia AE, any oral hypoesthesia AE, and discontinuations due to an AE will be considered Tier 2 endpoints. P-values (Tier 1 only) and 95% confidence intervals (Tier 1 and Tier 2) will be provided for between-treatment differences in the percentage of participants with events; these analyses will be performed using the Miettinen and Nurminen method (1985), an unconditional, asymptotic method [Miettinen, O. and Nurminen, M. 1985].

Table 7 Analysis Strategy for Safety Parameters

Safety Tier	Safety Endpoint [†]	p-Value	95% CI for Treatment Comparison	Descriptive Statistics
Tier 1	Any taste-related AE	X	X	X
Tier 2	Any oral paresthesia AE		X	X
	Any oral hypoesthesia AE		X	X
	Any AE		X	X
	Any SAE		X	X
	Any drug-related AE		X	X
	Any serious and drug-related AE		X	X
	Discontinuation due to AE		X	X
	Specific AEs, SOCs, or PDLCs [‡] (incidence ≥4 participants in one of the treatment groups)		X X	X X
Tier 3	Specific AEs, SOCs or PDLCs [‡] (incidence <4 participants in all of the treatment groups)			X
	Change from Baseline Results (Labs, ECGs, Vital Signs)			X
Abbreviations: AE = adverse event; CI = confidence interval; ECG = electrocardiogram; PDLC = pre-defined limit of change; SAE = serious adverse event; SOC = system organ class; X = results will be provided [†] Adverse Experience references refer to both Clinical and Laboratory AEs. [‡] Includes only those endpoints not pre-specified as Tier 1 or not already pre-specified as Tier-2 endpoints.				

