
• An AE is any untoward medical occurrence in a patient or clinical study participant, temporally associated with the use of study treatment, whether or not considered related to the study treatment.• NOTE: An AE can therefore be any unfavorable and unintended sign (including an abnormal laboratory finding), symptom, or disease (new or exacerbated) temporally associated with the use of a study treatment.• NOTE: for purposes of AE definition, study treatment (also referred to as Sponsor's product) includes any pharmaceutical product, biological product, vaccine, device, diagnostic agent or protocol specified procedure whether investigational (including placebo or active comparator product) or marketed, manufactured by, licensed by, provided by or distributed by the sponsor for human use in this study.

Events Meeting the AE Definition

• Any abnormal laboratory test results (hematology, clinical chemistry, or urinalysis) or other safety assessments (eg, ECG, radiological scans, vital signs measurements), including those that worsen from baseline, or are considered clinically significant in the medical and scientific judgment of the investigator.• Exacerbation of a chronic or intermittent pre-existing condition including either an increase in frequency and/or intensity of the condition.• New conditions detected or diagnosed after study treatment administration even though it may have been present before the start of the study.• Signs, symptoms, or the clinical sequelae of a suspected drug-drug interaction.• Signs, symptoms, or the clinical sequelae of a suspected overdose of either study treatment or a concomitant medication.• For all reports of overdose (whether accidental or intentional) with an associated adverse event, the AE term should reflect the clinical symptoms or abnormal test result. An overdose of study treatment without any associated clinical symptoms or abnormal laboratory results is reported using the terminology "accidental or intentional overdose without adverse effect."• Any new cancer or progression of existing cancer.

Events NOT Meeting the AE Definition

- Medical or surgical procedure (eg, endoscopy, appendectomy): the condition that leads to the procedure is the AE.
- Situations in which an untoward medical occurrence did not occur (social and/or convenience admission to a hospital).

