- Anticipated day-to-day fluctuations of pre-existing disease(s) or condition(s) present or detected at the start of the study that do not worsen.
- Surgery planned prior to informed consent to treat a pre-existing condition that has not worsened.
- Refer to Section 9.3.5 for protocol specific exceptions

Definition of SAE

If an event is not an AE per definition above, then it cannot be an SAE even if serious conditions are met

A SAE is defined as any untoward medical occurrence that, at any dose:

a. Results in death

b. Is life-threatening

- The term 'life-threatening' in the definition of 'serious' refers to an event in which the participant was at risk of death at the time of the event. It does not refer to an event, which hypothetically might have caused death, if it were more severe.

c. Requires inpatient hospitalization or prolongation of existing hospitalization

- Hospitalization is defined as an inpatient admission, regardless of length of stay, even if the hospitalization is a precautionary measure for continued observation. (Note: Hospitalization for an elective procedure to treat a pre-existing condition that has not worsened is not a serious adverse event. A pre-existing condition is a clinical condition that is diagnosed prior to the use of an MSD product and is documented in the patient's medical history.

d. Results in persistent or significant disability/incapacity

- The term disability means a substantial disruption of a person's ability to conduct normal life functions.
- This definition is not intended to include experiences of relatively minor medical significance such as uncomplicated headache, nausea, vomiting, diarrhea, influenza, and accidental trauma (eg, sprained ankle) which may interfere with or prevent everyday life functions but do not constitute a substantial disruption.

e. Is a congenital anomaly/birth defect

- in offspring of participant taking the product regardless of time to diagnosis

f. Other important medical events:

● Medical or scientific judgment should be exercised in deciding whether SAE reporting is appropriate in other situations such as important medical events that may not be immediately life-threatening or result in death or hospitalization but may jeopardize the participant or may require medical or surgical intervention to prevent one of the other outcomes listed in the above definition. These events should usually be considered serious.

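### The induced cold counts as an AE in every arm, so the any-AE comparison shows only about 15% to 52% of a drug-caused AE rate

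*Combined protocol and SAP*

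**What the plan says.** Section 9.3.5 of the protocol says: "There are no disease-related events and/or disease-related outcomes not qualifying as AEs or SAEs". In Appendix 4, the list of events that do not meet the AE definition ends with "Refer to Section 9.3.5 for protocol specific exceptions". The two places together leave no exemption.

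Appendix 4 defines an AE as "any untoward medical occurrence in a patient or clinical study participant, temporally associated with the use of study treatment, whether or not considered related" to that treatment. Section 9.3.1 sets the reporting window from randomization "through 14 days following cessation of treatment, all AEs, SAEs and other reportable safety events must be reported by the investigator". Inoculation takes place on Day 1, after randomization and immediately before the first dose (Sections 9.1.8 and 9.2.2), so the whole illness falls inside the window. The Appendix 4 exclusion for pre-existing conditions cannot apply, because participants are observed to be free of infection before Day 1 (Section 5.1).

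Section 3.3 says that "participants can expect to have a combination of one or more of the following symptoms after inoculation with the virus" and then lists nasal, eye and throat symptoms, headache, low-grade fever and cough.

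The count of participants with AEs is one of two secondary safety endpoints (Section 4). Section 10.6.2 places "the percentage of participants with any AE, a drug-related AE, an SAE" and several other categories in Tier 2, each with a between-group 95% CI. Table 7 has no row that sets the induced cold aside.

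**The concern.** The secondary safety objective concerns the drug. An any-AE comparison shows a drug effect only through participants who would otherwise have had no AE. When the procedure itself gives most participants in all arms an AE, few are left in whom a drug-caused event can change the count. A small difference with an interval spanning zero may then be read as good tolerability, when the row mostly reflects the virus.

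There is also a directional issue. Cough is both a reportable event and what the primary endpoint measures. If MK-7264 reduces cough, some participants on drug may leave the any-AE count because the drug worked, which would mask other events that it caused. A larger sample does not remove this.

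**Working it through.** **The plan's own figures.** Section 10.9: 50 × (1 − 0.20) = 40 evaluable per group, as stated. That is an efficacy figure. The safety population (Section 10.5.2) keeps everyone randomized and dosed, including non-shedders, so n = 50 per arm applies here. The Tier 2 threshold in Section 10.6.2 also reproduces: at 50 per arm the score statistic for 3 versus 0 events is 1.75 (interval includes zero), and for 4 versus 0 it is 2.03 (excludes zero).

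**Inputs.** From Section 5.4.1: 15-20% do not shed, so 80-85% do; cough occurs in 60-80% of those infected. The documents give no AE rate. Assumed: a drug-caused AE rate x of 20% or 30%, independent of the cold; the same cold-AE rate in both arms; and a residual background of 5% when cold events are set aside.

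**Background B of cold AEs among all dosed participants.**
- Cough alone: 0.80 × 0.60 = 48% to 0.85 × 0.80 = 68%.
- Every shedder has a cold AE and no non-shedder does: 80% to 85%.
- Left without a cold AE, of 50 per arm: 50 × (1 − B) = 26, 16, 10 and 7.5 at B = 48%, 68%, 80% and 85%.

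**Visible difference.** [1 − (1 − B)(1 − x)] − B = (1 − B)x. The fraction of x that remains visible runs from 1 − 0.85 = 15% to 1 − 0.48 = 52%.

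**CI half-width**, both arms near B: 1.96 × √(2B(1 − B)/50).

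**Chance that the 95% CI lies above zero.** Exact binomial enumeration of the score test at 50 per arm.

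| B | Difference at x = 20% (points) | Half-width (points) | Chance, x = 20% | Chance, x = 30% |
|---|---|---|---|---|
| 48% | 10.4 | 19.6 | 19.3% | 36.6% |
| 68% | 6.4 | 18.3 | 10.5% | 18.9% |
| 80% | 4.0 | 15.7 | 7.2% | 11.7% |
| 85% | 3.0 | 14.0 | 6.1% | 9.4% |

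**Cold events set aside.** With B = 5% and x = 20% the rates are 5% and 1 − 0.95 × 0.80 = 24%, a difference of 19 points. The half-width is 1.96 × √((0.05 × 0.95 + 0.24 × 0.76)/50) = 13 points, and the chance is 80.5% (97.4% at x = 30%).

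**Largest sample, 94 per arm, x = 20%.** The chances are 29.3%, 15.9%, 10.5% and 8.6% at B = 48%, 68%, 80% and 85%. The maximum sample size does not cure the dilution.

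**Offset from an antitussive effect.** If the cold-AE rate is B₀ on placebo and B₁ on drug, the any-AE difference is B₁ + (1 − B₁)x − B₀. It is zero when B₁ = (B₀ − x)/(1 − x). At x = 20%, B₀ = 48% gives B₁ = 35%, and B₀ = 80% gives B₁ = 75%. A fall of 13 or 5 points in the cold-AE rate would therefore cancel the drug-caused events in this row.

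**The case against.** Several objections are fair.

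- **Other safety outcomes remain.** The plan has a second secondary endpoint (discontinuation due to AEs), a Tier 1 taste composite, Tier 2 rows for oral paresthesia, oral hypoesthesia and drug-related AEs, and intervals for any term or organ class reaching 4 participants in a group. Taste effects are the most frequent known AEs (Section 3.3) and are isolated from cold symptoms. This stands, and it limits the point to the any-AE row.
- **The trial is exploratory.** The intervals are descriptive and no formal test is planned (Sections 10.6.2 and 10.8). This also stands, so the chances above are illustrative. A descriptive interval can still be misread.
- **The recording rules are softer than they look.** Appendix 4 replaces symptoms by a diagnosis where one is established. That does not alter a count of participants. A note there also speaks of "any unfavorable and unintended sign", and unintended fits poorly with a cold induced on purpose. If some sites therefore recorded less, the background would become site-dependent.
- **The offset may be small.** A participant leaves the count only if cough was the sole AE; one other symptom or a URTI entry keeps them in. This stands, which is why the offset is given only as a break-even.

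A reader might go further and infer that the drug-related row is swamped too, because Appendix 4 counts a "diagnostic agent or protocol specified procedure whether investigational" or marketed as study treatment for the AE definition. The same sentence adds a condition of manufacture, licence, provision or distribution by the sponsor, and the protocol does not say that the sponsor supplies the virus. Table 1 lists only MK-7264 and placebo. The causality guidance answers no when another cause is more likely. A reader might also infer that the nightly questionnaires turn symptom scores into AEs. Section 9.2.4 only asks staff to clarify relevant comments that point to possible AEs.

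**Conclusion.** The concern holds for the any-AE endpoint and its Tier 2 row. The induced cold puts a background of about 48% to 85% under both arms, and a drug-caused rate appears at 15% to 52% of its size: 3 to 10 points for an assumed 20%, against a half-width of about 14 to 20 points at 50 per arm.

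It is tempting to say that the endpoint is saturated. The documents do not show that. They state no AE rate, and on their own percentages between 7.5 and 26 of 50 participants per arm would have no cold AE. Other AEs, or symptoms in non-shedders, could raise the any-AE rate further, but nothing in the protocol puts it at the ceiling. Nor is full AE capture under Section 9.3.5 an error in itself. What is missing is a summary that separates the induced illness from everything else.

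The shedding and cough percentages are the protocol's. The drug-caused rate, its independence from the cold, equal cold-AE rates in the arms and the 5% residual background are assumptions.

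**What to change.** Keep collecting and reporting all AEs, and keep the any-AE row. In Section 10.6.2 and Table 7, add one Tier 2 row for participants with any AE other than HRV-16 symptoms. Define the excluded terms as the Section 3.3 symptom list plus URTI and rhinovirus infection terms, and fix them before unblinding; the supplemental SAP is a suitable place. State that the tolerability conclusion reads this row alongside the any-AE row.

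The cost is a fixed term list and one table row, with no change to safety reporting. The downside is that a drug-caused event under a listed term, such as headache, would appear only in the unrestricted row and the term-level tables. That is why both rows are needed.
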